#### Primary

- Change in MELD score at 6 weeks
- Incidence of serious adverse events (SAEs) during the treatment phase

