#### 1.3.1 Rationale for Dose and Duration

Our choice to administer OCA for 42 days is based on the study by Mudaliar et al (33) which showed significant reduction in C4 levels at day 42, indicating OCA's efficacy in reducing bile salt synthesis by that time point.

We chose 10 mg dose to investigate because (a) it is among the doses that is being used in ongoing PBC and non-alcoholic steatohepatitis (NASH) clinical trials, (b) it is among the doses that is being investigated to treat portal hypertension in subjects with alcoholic cirrhosis in the United Kingdom (<http://www.controlled-trials.com/ISRCTN22662520>), and (c) in one study, although OCA and FGF19 levels increased in a dose-dependent fashion, OCA administered at a 10 mg dose had similar effect on serum C4 levels as OCA 50 mg (reduction in C4 concentration, reflecting inhibition of bile salt synthesis of - 6.8 ng/ml vs. -6.5 ng/ml, p=ns).

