### Secondary

- Any SAEs during the follow-up phase
- SAEs attributable to the study medicine during the treatment and follow-up

phases

- AEs and discontinuation rates during the treatment and follow-up phases
- Change in MELD score at 90 and 180 days
- Change in Child-Pugh score at 6 weeks and at 90 and 180 days
- Mortality rate at Week 6 and at 90 and 180 days
- Rates of hospitalization and lengths of stay
- Changes in intestinal inflammation and bacterial translocation
- Changes in serum oxidative stress, cytokines, and activation of innate immunity.

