## **5.3 DOSE, ADMINISTRATION AND BLINDING**

Two (2) treatment groups will be evaluated in the trial: (a) placebo or (b) 10 mg OCA. Study medication will be administered orally, once daily for 6 weeks (42 days) during the study. Each daily dose will be made up of 1 tablet.

Patients will be instructed to begin dosing on the day after the Day 0 visit (i.e., on Day 1) and to take study medication with water, approximately 30 minutes prior to breakfast. Patients must be instructed to swallow the tablet whole; they must not chew, divide, or crush the tablet.

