**7. EFFICACY EVALUATIONS**

**TO ASSESS THE EFFECTS OF OCA IN PATIENTS WITH MODERATELY SEVERE AH ON:**

**PRIMARY OBJECTIVE**

- Changes in MELD score at 6 weeks of treatment
- Incidence of SAEs during the treatment phase

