## 10. STATISTICAL METHODS

### 10.1. ANALYSIS SETS

Primary end point: Analysis will be based on intention-to-treat principle. We will evaluate the main outcome, change in MELD score at day 42, in the framework of the repeated measurements analysis of covariance (ANCOVA) model. Specifically, MELD score at each follow-up visit will be used as the outcome variable. The main predictor is treatment group (GROUP). We will adjust for time (visit) and baseline MELD score and include the interaction between GROUP and visit. The interaction term allows evaluation of GROUP difference at each visit. The main comparison is the differences of MELD score change at day # 28 between two groups. A random intercept will be used to adjust for the correlation among the observations from the same subject. We will also evaluate the GROUP difference at 90 and 180 days in the framework of above repeated ANCOVA model.

SAEs during treatment: The primary analysis is to compare the proportion of patients having at least one SAE during the treatment period between the two groups using Chi-square tests. *SAE during follow-up* will be analyzed similarly. Other safety outcomes include AEs, discontinuations, pre-defined laboratory abnormalities, and predefined EKG abnormalities. Other continuous outcomes will be analyzed in a similar way to MELD score, binary outcomes will be analyzed in a similar way to SAE, and censored time-to-event outcomes will be analyzed using appropriate survival analysis tools (e.g., Kaplan-Meier plots, Cox models).

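### Section 10.1 defines the primary MELD test at day 28, although its own opening and every statement of the primary objective put it at day 42; section 10.2 gives power and dropout for day 28 only

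*Combined protocol and SAP*

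**What the plan says.** Statements that put the primary MELD outcome at 6 weeks or day 42:

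- Synopsis (Objectives, Primary) and section 2 (Primary): "Change in MELD score at 6 weeks".
- Section 7 (Primary objective): "Changes in MELD score at 6 weeks of treatment".
- Section 10.1, opening of the primary end point paragraph: "We will evaluate the main outcome, change in MELD score at day 42".
- Section 5.3 equates 6 weeks with 42 days: "Study medication will be administered orally, once daily for 6 weeks (42 days) during the study". Section 1.3.1 justifies that length by a C4 effect seen at day 42 in an earlier study: "Our choice to administer OCA for 42 days is based on the study".

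Statements that put it at day 28:

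- Section 10.1, later in the same paragraph: "The main comparison is the differences of MELD score change at day # 28 between two groups".
- Section 10.2 computes power for the change from baseline to day 28 and assumes 10% dropout at day 28, leaving 27 of 30 per arm. It gives no figures for day 42.

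The secondary MELD objective is "Change in MELD score at 90 and 180 days". Table 1 and sections 6.2.6 and 6.2.7 schedule MELD separately at days 28 and 42. On the group-by-visit term, section 10.1 says: "The interaction term allows evaluation of GROUP difference at each visit".

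**The concern.** The visit at which the primary contrast is read is a basic element of an analysis plan, and here one paragraph gives two answers. Because the model includes a group-by-visit interaction, the day-28 and day-42 contrasts are separate estimates with separate p-values. An analyst who follows the sentence defining the comparison would report as primary a result at a visit that no objective names, two weeks before treatment ends. An analyst who follows the opening sentence would report day 42. If the matter is settled only after unblinding, nobody can show that the choice was independent of the results.

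The day-28 basis of section 10.2 is a related but lesser defect. It means that the protocol states no power and no expected loss for the outcome its objectives name.

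**Working it through.** **1. Which visit is intended.** Four statements name 6 weeks or day 42: synopsis, section 2, section 7 and the opening of 10.1. One sentence in 10.1 and the power basis in 10.2 name day 28. Nothing in the protocol explains day 28 as the main comparison. The amendment summaries in the appendices list no change to section 10, so both readings are current text.

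**2. The plan's own power figure.** Inputs from section 10.2: 30 per arm, 10% dropout, two-sample t-test, 80% power, effect 0.78 SD. Alpha and sidedness are not stated.

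- Evaluable per arm: 30 × 0.90 = 27.
- Noncentrality = d × √(n/2) = 0.78 × √13.5 = 2.866, with 2 × 27 − 2 = 52 degrees of freedom.
- Two-sided 5% gives power 80.3% and a detectable effect at 80% power of 0.777 SD, which matches the stated 0.78.
- One-sided 5% gives a detectable effect of 0.686 SD and two-sided 2.5% gives 0.860 SD. Neither matches, so two-sided 5% is inferred.

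The arithmetic in 10.2 is sound; only the visit is wrong.

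**3. The same calculation at day 42.** The documents give no day-42 loss, so a range is shown (two-sided 5%, whole patients rounded down). As a reference point, 10% loss per 28 days continued at a constant rate to day 42 gives 1 − 0.9^(42/28) = 14.6%.

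| Loss by day 42 (assumed) | Evaluable per arm | Power at 0.78 SD | Detectable effect, 80% power |
|---|---|---|---|
| 10% | 27 | 80.3% | 0.78 SD |
| 13% | 26 | 78.8% | 0.79 SD |
| 15% | 25 | 77.1% | 0.81 SD |
| 20% | 24 | 75.3% | 0.83 SD |

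**4. What an open choice of visit would do to the error rate.** Let Z28 and Z42 be bivariate standard normal under the null, with correlation r. If success is claimed when either |Z| exceeds 1.96, the false-positive rate is 1 − P(|Z28| ≤ 1.96 and |Z42| ≤ 1.96). If one visit is fixed beforehand it is 5%.

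**5. How often the two visits would disagree.** Assume a true effect of 0.78 SD at both visits and 27 per arm at both. Each Z then has mean 2.866, and P(exactly one significant) = P(either) − P(both), by normal approximation.

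| r (assumed) | False-positive rate, either visit | Exactly one visit significant |
|---|---|---|
| 0.9 | 7.0% | 9.5% |
| 0.8 | 7.8% | 13.4% |
| 0.7 | 8.3% | 16.4% |
| 0.5 | 9.1% | 21.2% |

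**The case against.** The strongest reply is that the weight of the text favours day 42. The three statements of the objective and the first sentence of 10.1 agree, and that sentence already ties the repeated-measures model to day 42. Nothing suggests that anyone means to pick a visit after the fact. This limits the practical risk. It does not remove the contradiction, because the conflicting sentence is the one that says what is tested, and section 10.2 repeats day 28.

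Four further points stand as qualifications:

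- The error-rate and disagreement figures are illustrations. Alpha, the correlations and equal effects at both visits are assumptions, so the finding rests on the text rather than on these numbers.
- The t-test figures for day 42 are probably conservative. Section 10.2 itself says that the repeated-measures ANCOVA is more powerful. With equal variance at baseline and day 42, a single-visit ANCOVA has residual SD equal to √((1+ρ)/2) times the SD of change. At 25 per arm, power for 0.78 SD of change is then about 88%, 83% or 79% for a baseline-to-day-42 correlation ρ of 0.5, 0.7 or 0.9. The shortfall below 80% may not arise.
- Loss by day 42 may stay near 10%. Section 4.3.3 keeps patients who stop study drug but remain in the study on the visit schedule. Section 6.2.9 asks those who withdraw or stop treatment early to complete the day-42 assessments. These two provisions may differ on timing and should be read together when the loss assumption is set.
- The 5% level concerns the MELD test alone. SAE incidence is listed as a second primary outcome, and no allocation of alpha is given.

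**Conclusion.** The concern holds. Section 10.1 contradicts itself and the objectives on the visit of the primary MELD contrast, and section 10.2 follows the wrong visit. This must be corrected before unblinding.

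The size depends on how the conflict is resolved. Settled in advance, it costs nothing in error rate. Left open and settled on the results, it would take an assumed two-sided 5% to about 7.0–9.1%. With a real effect of 0.78 SD at both visits, the choice of visit would decide significance in roughly 9–21% of trials. Both ranges assume correlations of 0.9 down to 0.5.

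The effect on stated power is small: unchanged at 80% if loss by day 42 is 10%, and about 75–77% on the t-test basis if it is 15–20%. No SD in MELD points is given, so whether the SD of change differs between days 28 and 42 cannot be checked.

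**What to change.** Before unblinding:

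1. In section 10.1, replace day 28 with day 42 in the sentence that defines the main comparison, and state that this is the single primary MELD contrast. The day-28 contrast remains available from the same model as a supporting result.
2. In section 10.2, restate the power for change from baseline to day 42, giving the assumed loss by day 42 and the alpha with its sidedness. With 30 randomised per arm and two-sided 5%, that is 80% power at 0.78 SD if loss is 10%, or about 77% (0.81 SD detectable) if loss is about 15%.

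The cost is one sentence in 10.1 and a rewritten power statement in 10.2, with no extra visits or data. The correction itself does not require more patients. If loss of about 15% is expected and the sponsor wants 27 evaluable per arm on the t-test basis, 32 per arm would be needed (32 × 0.85 = 27.2). Whether 77% on that conservative basis is acceptable is for the sponsor to judge. The only downside is a possibly slightly less favourable stated power.

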## Secondary Objectives

- Any SAEs during the follow-up phase
- SAEs attributable to the study medicine during the treatment and follow-up phases
- AEs and discontinuation rates during the treatment and follow-up phases
- Change in MELD score at 90 and 180 days
- Change in Child-Pugh score at 6 weeks and 90 and 180 days
- Mortality rate at 6 weeks, 90 days and 180 days
- Rates of hospitalization and lengths of stay
- Changes in intestinal inflammation and bacterial translocation
- Changes in serum oxidative stress, cytokines, and activation of innate immunity.

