### 10.2. DETERMINATION OF SAMPLE SIZE

We examined the power of testing the difference in change of MELD score from baseline to day 28 with sample size of 30 in each group. Assuming a 10% drop out rate at day 28, we will have 27 subjects in each group. Using a two-sample t-test, we will have 80% power to detect any difference in effect size  $\geq 78\%$  of one standard deviation (smallest detectable effect size=0.78). The analysis using repeated-measurement ANCOVA will be more powerful than a two-sample t-test.

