#### **10.5. HANDLING OF MISSING DATA**

Missing values will not be imputed and only observed values will be used in data analyses and presentations.

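### Follow-up SAEs are compared by chi-square on proportions with no denominator or allowance for unequal time at risk, and 90/180-day mortality is assigned to no method

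*Combined protocol and SAP*

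**What the plan says.** Section 10.1 (Analysis Sets) defines the primary SAE analysis as being to "compare the proportion of patients having at least one SAE during the treatment period between the two groups using Chi-square tests". SAEs in the follow-up phase "will be analyzed similarly. Other safety outcomes include AEs, discontinuations". Two general rules follow: "binary outcomes will be analyzed in a similar way to SAE", and "censored time-to-event outcomes will be analyzed using appropriate survival analysis tools", with Kaplan-Meier plots and Cox models as examples. No outcome is named as belonging to the time-to-event group.

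Section 10.5 (Handling of Missing Data) states: "Missing values will not be imputed and only observed values will be used in data analyses and presentations". The intention-to-treat principle appears in 10.1 under the primary end point only.

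Section 2 lists as secondary objectives any SAE in the follow-up phase and "Mortality rate at Week 6 and at 90 and 180 days"; Section 7 repeats the latter as "Mortality rate at 6 weeks, 90 days and 180 days". The only statement about loss is in Section 10.2: "Assuming a 10% drop out rate at day 28", applied to both arms.

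**The concern.** A chi-square on proportions treats every patient in the denominator as equally observed. That is a fair approximation over 42 days. It is weaker over the 138 days from Day 42 to Day 180, when patients may already have died or left, or may leave part-way through. The plan does not say whether a patient who leaves event-free at, say, Day 95 counts as having had no follow-up SAE or is removed.

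The early-termination rule in Section 6.2.9 adds to the uncertainty. Someone leaving during follow-up is asked to complete the Day 180 assessments at exit, and could then be tabulated like a patient observed to Day 180.

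At stake is a named secondary safety outcome in a trial of 30 per arm. Two defensible readings of one sentence can give differences of opposite sign from the same data. For mortality, the gap is that either general rule in 10.1 could be applied.

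**Working it through.** **The plan's own figure.** 30 × 0.9 = 27 per arm. A two-sample t-test with effect size 0.78 and two-sided alpha 0.05 (assumed; Section 10 does not state it) has 80.3% power by the noncentral t distribution, against 80% stated. The figure reproduces, but concerns MELD only. The plan gives no figure for SAEs or mortality.

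**Inputs.** From the documents: 30 per arm; follow-up of 180 − 42 = 138 days; 10% loss by Day 28 in both arms. Assumed: SAE risks, losses during follow-up, any difference in loss between arms, and that all 30 per arm enter follow-up.

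**Loss if the Day 28 rate continued.** 1 − 0.9^(d/28) gives 15% at Day 42, 29% at Day 90 and 49% at Day 180. Over the follow-up phase alone, 1 − 0.9^(138/28) = 40.5%, the same in both arms.

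**Model.** Independent exponential event and loss times. For event risk R and loss D over the phase, λ = −ln(1−R) and m = −ln(1−D).
- All randomised, event-free losses counted as no event: A = λ/(λ+m) × (1 − e^−(λ+m)).
- Event-free losses dropped: B = A / (A + e^−(λ+m)).

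**Equal risk 50%, loss 20% versus 50%.** λ = 0.693; m = 0.223 and 0.693.
- A: 0.693/0.916 × 0.600 = 45.4%, and 0.693/1.386 × 0.750 = 37.5%. The high-loss arm looks 7.9 points safer.
- B: 0.454/(0.454 + 0.400) = 53.2%, and 0.375/(0.375 + 0.250) = 60.0%. The high-loss arm looks 6.8 points worse.
- Simulated rejection at 30 per arm: 9.3% under A, 8.2% under B, 5.6% for log-rank. A separate set of 20,000 runs gave 9.5%, 7.4% and 5.0%.

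**True excess, 30% versus 60%, loss 20% versus 50%, heavier in the 60% arm.** A gives 27.1% versus 45.5%; B gives 32.6% versus 69.5%. Power is about 31% under A, 71% under B and 59% for log-rank. The higher power under B reflects an overstated difference (36.9 points against a true 30).

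**Same excess, equal loss of 40.5%.** A: 23.8% versus 48.6%, so 30 points read as 24.9; power is about 51%, against 57% for log-rank. With no true difference and equal loss, rejection stays near 5% under either denominator.

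**Milder imbalance, equal risk 30%, loss 10% versus 30%.** A: 28.6% versus 25.5% (−3.1 points). B: 31.2% versus 34.2% (+3.0 points). Total rejection is about 5.7% either way.

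**Informative loss, same risk and losses, all at the start of follow-up.** If those lost have twice the event hazard, completers-only proportions are 28.0% versus 24.5%. With half the hazard they are 31.4% versus 34.6%.

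**Mortality.** True 180-day risk 15%, loss 49%, status unknown after loss. Deaths seen: 0.163/0.840 × 0.568 = 11.0%. Known alive: 43.2%. Observed-only: 0.110/(0.110 + 0.432) = 20.3%.

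**The case against.** Several points on the other side are sound.

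- **Direction.** A reader might infer that the arm losing more patients will look safer. The documents do not support that. It needs lost patients to be counted as event-free, or to be at higher risk than those who stay. If event-free losses are dropped and loss is unrelated to risk, the bias is zero (all loss at the start) or reversed.
- **Death.** A reader might infer that deaths in follow-up vanish from the count. They do not: Section 9.2.1 makes death an SAE, and Section 9.1.1 records AEs to Day 180. Only deaths before follow-up remove patients from risk, and these already count in the 6-week comparison.
- **Mortality.** A reader might infer that chi-square on observed cases is the stated plan. It is not; 10.1 equally permits Kaplan-Meier and Cox. This is an ambiguity to close.
- **Unequal loss.** It is assumed. The plan's 10% is a sample-size allowance common to both arms, and equal loss does not inflate the false-positive rate.
- **Safeguards.** Section 4.3.3 keeps patients who stop study medication but remain in the study on the visit schedule, and 6.2.9 asks early leavers for a final assessment. These reduce loss without removing it.

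What remains is that 10.1 expressly sends follow-up SAEs to the proportion method, leaves the denominator open and ignores time at risk. Nothing elsewhere supplies either.

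**Conclusion.** The concern holds as a gap that can attenuate the follow-up SAE comparison or bias it in either direction. Under the assumed 20% versus 50% loss, the bias is about −8 or +7 points depending on the denominator, with chi-square rejection of roughly 7% to 10% against 5% to 6% for log-rank. At 10% versus 30% it is about 3 points either way, with little inflation. Under equal loss the problem is attenuation, and only when all randomised patients are counted.

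For mortality the method is unassigned; an observed-only proportion would overstate a true 15% as about 20% at 49% loss.

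All sizes rest on assumed risks and losses, and on loss unrelated to risk except where stated. They illustrate the problem and do not forecast this trial. The change is worth making because the better tools are already named in 10.1.

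**What to change.** In Section 10.1, replace the sentence that analyses follow-up SAEs like treatment-phase SAEs with:

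1. Time from Day 42 to first follow-up SAE, among patients alive and in the study at Day 42, censored at last contact. Use Kaplan-Meier with log-rank or Cox. Deaths in follow-up count because they are already SAEs. Also report SAEs per patient-month at risk by arm.
2. As a supportive analysis, time from randomisation to first SAE through Day 180 in all randomised patients. The first analysis conditions on reaching Day 42; this one keeps everyone. It should not replace the first, because it merges the two phases that the objectives separate.
3. Mortality at Days 42, 90 and 180 as Kaplan-Meier estimates with a log-rank test in all randomised patients.
4. One sensitivity analysis for informative loss, since these methods assume non-informative censoring.

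The 6-week primary SAE comparison stays as it is.

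The cost is SAP wording and a little more analysis. AE timing, deaths, visit dates and withdrawal dates are already to be recorded (Sections 9.1.1, 8.5 and 4.3.3, and the source-document list in 10.4.1).

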### 10.2. DETERMINATION OF SAMPLE SIZE

We examined the power of testing the difference in change of MELD score from baseline to day 28 with sample size of 30 in each group. Assuming a 10% drop out rate at day 28, we will have 27 subjects in each group. Using a two-sample t-test, we will have 80% power to detect any difference in effect size  $\geq 78\%$  of one standard deviation (smallest detectable effect size=0.78). The analysis using repeated-measurement ANCOVA will be more powerful than a two-sample t-test.

### **10.3. SAFETY ANALYSIS**

Descriptive statistics will be used to summarize safety data to allow a comparison between groups.

Safety data, including AEs, clinical and laboratory observations and physical examination findings, and other safety related outcomes will be summarized by treatment group.

#### **10.3.1. AEs**

AEs will be labeled according to standard medical terminology using the case report forms provided. Summary tables of treatment-emergent AEs will be provided. A TEAE is any AE that newly appeared, increased in frequency, or worsened in severity following initiation of study medication. The incidence of TEAEs will be tabulated by system organ class and preferred term for each treatment group, and by severity and relationship to treatment. Tables of TEAEs leading to study medication discontinuation and SAEs will be provided.

#### **10.3.2. Clinical Laboratory Evaluations**

Descriptive statistics summarizing central laboratory data (hematology, chemistry, and coagulogram) will be presented for all trial visits. Changes from pretreatment to each trial visit will also be summarized by treatment group/arm.

#### **10.3.3. Additional Safety and Clinical Findings**

Additional safety assessments include vital signs, physical examinations, and ECGs. Descriptive statistics of the vital sign and ECG parameters will be presented by treatment group and trial visit, as well as the change from BL at each visit. The percentage of patients in each treatment group with clinically significant abnormal ECG findings will be summarized.

